	- 130 patients that should complete the study (65 patients in each group).			
Study aim	The aim of this double-blinded controlled study is to assess clinical			
	efficacy and safety of intra-articular polyacrylamide hydrogel with ions			
	of silver in comparison with placebo (0.9% sodium chloride solution) in Kellgren Lawrence radiological grade II-III knee osteoarthritis			
	Religion Lawrence radiological grade 11-111 knee osteoaruntus			
Study goals	Assessment of a change in knee joint functionality, stifnes and			
	joint pain intensity estimated per the corresponding subscales			
	and total arthritis index score developed by Western Ontario			
	and McMaster Universities (WOMAC) during administration of			
	intra-articular MD NOLTREX TM in comparison with placebo			

(0.9% sodium chloride solution) in Kellgren Lawrence radiological grade II-III knee osteoarthritis;

- Assessment of the need in paracetamol and NSAID (in case of ineffective therapy with paracetamol) intake to relieve the knee pain during administration of intra-articular MD NOLTREXTM in comparison with placebo (0.9% sodium chloride solution) in Kellgren Lawrence radiological grade II-III knee osteoarthritis;
- Assessment of efficacy of MD NOLTREXTM in comparison with placebo (0.9% sodium chloride solution) in Kellgren Lawrence radiological grade II-III knee osteoarthritis as subjectively assessed by a patient;
- Assessment of efficacy of MD NOLTREXTM in comparison with placebo (0.9% sodium chloride solution) in Kellgren Lawrence radiological grade II-III knee osteoarthritis as subjectively assessed by the investigator;
- Assessment of **safety** of intra-articular MD NOLTREX[™] in comparison with placebo (0.9% sodium chloride solution) in Kellgren Lawrence radiological grade II-III knee osteoarthritis.

Study methodology

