- Investigator's assessment of the treatment efficacy, OEI-w₂₅ value (per the scale from 1 evident aggravation to 6 significant improvement);
- Assessment of the total number of paracetamol tablets taken per the patient diary (one tablet = 500 mg) starting from day 1, value PARACETAMOL-w₂₅;
- Assessment of the total number of NSAID tablets taken per the patient diary starting from day 1, value NSAID-w₂₅,
- Complete blood count;
- Blood biochemistry: glucose, ALT, AST, ALP, GGTP, total bilirubin, creatinine, uric acid;
- Coagulogram (APTT, PT, prothrombin index, fibrinogen);
- Urine analysis;
- Express urine pregnancy test for women with the preserved reproductive potential;
- AE assessment.
- In case of planned completion of the study and completion of all procedures provided in the clinical study protocol, the patient will be provided with studied medical device NOLTREX regardless of the treatment group to which the patient was assigned. In this case the patient will receive 4 packages of NOLTREX which corresponds to one treatment course.

Unscheduled visit

Unscheduled visits will be made as necessary, for example, in the event of aggravation of the studied medical condition, AE or intolerability of the study MD or placebo therapy. When an unscheduled visit is made, regardless of its reason, the investigator makes the following procedures and completes corresponding eCRF pages (Unscheduled visit):

- Collection of complaints and medical history;
- Recording of concomitant therapy;
- Measurement of body weight;
- Assessment of vital signs (BP, HR, RR, body temperature);

- Physical joint examination;
- Assessment of the patient diary;
- AE assessment.

If clinically indicated and meeting the criteria, any of the study procedures can be additionally made on the unscheduled visit by the decision of the Principal Investigator.

Premature study discontinuation visit

• On the premature study discontinuation visit, the same procedures are made as on Visit 5

Main parameters of efficacy and safety assessment

rs of Primary endpoint – change of the total WOMAC score (WOMAC-T) safety on Visit 5 (Week 25) in comparison with baseline on visit 1 (Week 1).

Secondary endpoints:

- Change of the total WOMAC score (WOMAC-T) on Visit 4 (Week 13) in comparison with baseline on Visit 1 (Week 1);
- Change of the pain subscale score (WOMAC-A) on Visit 3 (Week
 6), Visit 4 (Week 13) and Visit 5 (Week 25) and in comparison with baseline on Visit 1 (Week 1);

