- 30) Severe decompensated chronic or acute diseases and other conditions which, by the opinion of the study physician, may preclude the patient's participation in the study or affect the study results.

Subject exclusion criteria

- Ethics Committee, regulatory bodies or the Sponsor terminate the study or participation of the clinical site in the study for any reasons;
 - Need in paracetamol or NSAID intake due to knee osteoarthritis 4 days a week or more during 2 successive weeks;
 - 3) The investigator makes the decision that a patient should discontinue the study in the best interests of the patient;
 - Informed consent revocation (patient's unwillingness to continue the study);
 - 5) Major deviation from the study protocol;
 - Individual intolerability or contraindications to the study MD, placebo or paracetamol;
 - AE/SAE which requires examination and/or treatment affecting significantly the study procedures (in particular, development of active arthritis or hemarthrosis of the target knee joint);

- 8) Erroneous study inclusion (for example, the patient was included with a violation of the protocol inclusion/non-inclusion criteria);
- 9) A patient has non-inclusion criteria during the study;
- 10) A patient takes/needs additional treatment which can affect the study result or patient's safety (see section "Disallowed concomitant therapy");
- 11) Other conditions or events which require, by the opinion of the study physician, the patient's exclusion from the study.
- 12) Injury of the studied joint.

Disallowed concomitant therapy

- 1. Glucocorticosteroids in any dosage form;
- 2. Any intra-articular or peri-articular injections, physical therapy, as well other therapeutic or rehabilitation measures for knee osteoarthritis, except the study procedures;
- NSAIDs and analgesics including the local ones (except for paracetamol and NSAIDs permitted by the protocol in cases when paracetamol is ineffective);
- 4. Paracetamol intake in dose over 4000 mg a day;
- 5. the use of one of the NSAIDs permitted by the Protocol in doses exceeding those permitted by the Protocol (permitted drugs and doses: diclofenac potassium 50 mg 2 times a day, diclofenac sodium tablets 75 mg 2 times a day, naproxen tablets 500 mg 2 times a day, naproxen sodium tablets 550 mg 2 times a day, meloxicam tablets 7.5 mg once a day, celecoxib tablets 200 mg 2 times a day);
- use of NSAID in combination with paracetamol or combination of two or more NSAID;

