#### 2.1.3 Analysis of secondary efficacy parameters

An analysis of the following secondary efficacy parameters is planned:

- Changing the overall score on the WOMAC scale (WOMAC-T) on Visit 4 (week 13) compared to the basal value on Visit 1 (week 1);
- The change in score on the subscale of pain (WOMAC-A) on Visit 3 (week 6), Visit 4 (week 13) and Visit 5 (week 25) and compared with the basal value on Visit 1 (week 1);
- The change in the score for the stiffness (WOMAC-B) and functionality (WOMAC-C) on Visit 3 (week 6), Visit 4 (week 13) and Visit 5 (week 25) compared to the basal value on Visit 1 (week 1);
- Evaluation of the treatment efficacy by the patient, the value OEP (on a scale of 1 a clear deterioration to 6 a significant improvement) at visits 3, 4 and 5 (OEP-w6, OEP-w13, OEP-w25);
- Evaluation of the effectiveness of treatment by the investigator, the value OEI (on a scale of 1 a clear deterioration to 6 a significant improvement) on visits 3, 4 and 5 (indicators OEI-w6, OEI-w13, OEI-w25);
- Assessment as per patient diary of the total number of paracetamol tablets taken (one tablet = 500 mg) starting on day 1, on visits 3, 4 and 5 (PARACETAMOL-w6, PARACETAMOL-w13 and PARACETAMOL-w25, respectively);
- Assessment per patient diary of the total number of NSAID tablets, starting on day 1, at visits 3, 4, 5 (values NSAID-w6, NSAID-w13 and NSAID-w25, respectively)
- Drop-out rate due to safety (exclusion criteria 2, 3, 6, 7);
- Drop-out rate due to low patient adherence to treatment (criteria 4 and 5).

For secondary efficacy parameters, the following statistical analysis methods are planned:

- For quantitative indicators, an analysis similar to the analysis of the primary endpoint (covariance analysis) followed by the identification of groups with significant differences using Tukey's HSD.
- For frequency indicators (segments) comparison of groups using the  $\chi^2$  criterion ("chi-square").

Analysis of secondary efficacy parameters will be conducted on the ITT population (main analysis) and on the PP population (additional analysis).

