# 2.3 Planned number of participants in a clinical trial with justification of sample size

The calculation of the sample size is based on the study results of the medical device NOLTREX TM for OA (osteoarthritis) of the knee joint (N. V. Zagorodny et al. The use of new biopolymer material Noltrex in the complex treatment of patients with gonarthrosis. 2012, t. 17, No. 6, p. 49-52)[3]. Application in this study during the first 10 days of NSAID Movalis does not affect the assessment of results after 13 and 25 weeks.

As the primary endpoint in the study the change in total score on the WOMAC scale in the affected joint (WOMAC total) was chosen, at Visit 7 (week 25) compared to the basal value at Visit 1 (week 1). The choice of "Week 25" assessment point is related to the fact that in the above study the effect of medical device NOLTREX TM was maximal after 6 months from the injection, and then the effect of the treatment was decreasing. An additional endpoint - a change in the total score on the WOMAC

scale (WOMAC total) at Visit 6 (week 13) compared to the basal value at Visit 1 (week 1) will be used to assess the onset of the effect of medical device after 3 months from the injection.

For the calculations the following assumptions were used:

- 1) Two groups (fixed factor A) medical device NOLTREXTM and placebo
- 2) Baseline of WOMAC level and the total dose of NSAIDs received in the duration of study as covariates
- 3) Effect size 0.25: calculated on the basis of data from the above publication, in which the magnitude of differences between groups, taking into account the variability, was up to 100 points, and the variability (standard deviation) up to 400 points
- 4) Level of significance = 5% (type I error  $\alpha$  = 0.05)
- 5) Power 80% (type II error  $\beta$  = 0.20)
- 6) Statistical model covariance analysis (adjusted for the initial value) with fixed factors of the group
- 7) Drop-outs during the study will not exceed 10%.
- 8) Drop-out during inclusion period (screening) will not exceed 15%.

Calculations of the sample size (the number of completed cases) were performed using the G\*Power 3.1.9.2 software package with the above assumptions:

F tests - ANCOVA: Fixed effects, main effects and interactions

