## 2.6 Procedures to count the missing, non-analyzable and questionable data

During the monitoring visits to the clinical center, the monitoring specialists authorized by the sponsor will conduct an analysis of patient's eCRF to identify any lack of necessary data. In the absence of data in the eCRF and the availability of relevant information in the primary documentation, the questions to the investigators and instructions for eliminating the inconsistencies will be formulated.

The statistician, authorized by the sponsor, and the principal investigator, when checking the database of research results, will analyze for the presence of dubious, missing and non-analyzable data, and will also formulate questions to investigators.

Investigators, if possible, will eliminate the identified errors in eCRF and inform the main investigator and authorized representatives of the sponsor about this. If the detected errors in the data cannot be eliminated after the completion of patient participation in the study, the statistical analysis of the data will be used to analyze the sensitivity of the resulting parameters to the doubtful data found. Information about the missing, doubtful and non-analyzable data will be presented in the final clinical trial report.

The missing data for the primary efficacy parameter will be replenished by the last observation carried forward (LOCF) method (transfer of data from the last available observation point to the point for the main analysis).

For the remaining parameters of efficacy, safety and tolerability, data replenishment is not provided.

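### Cumulative paracetamol counts are a biased measure of rescue need, in either direction, because NSAID step-up and criterion 2 exclusion stop the count

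*SAP*

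**What the plan says.** The second study goal in the Protocol synopsis is the "Assessment of the need in paracetamol and NSAID (in case of ineffective therapy with paracetamol) intake to relieve the knee pain". SAP 2.1.3 serves it with two separate cumulative endpoints, each read at Weeks 6, 13 and 25: the "Assessment as per patient diary of the total number of paracetamol tablets taken (one tablet = 500 mg) starting on day 1", and the "Assessment per patient diary of the total number of NSAID tablets, starting on day 1, at visits 3, 4, 5". Both are quantitative, so both are compared by covariance analysis in the manner of the primary endpoint.

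Three rules determine how long paracetamol tablets can accumulate:

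- **Step-up.** The list of disallowed therapy bars analgesics "except for paracetamol and NSAIDs permitted by the protocol in cases when paracetamol is ineffective". The same list bars taking an NSAID together with paracetamol.
- **Exclusion criterion 2.** A patient who needs rescue on 4 or more days a week in two consecutive weeks is excluded.
- **Early exit.** "On the premature study discontinuation visit, the same procedures are made as on Visit 5", so a total to date is recorded. For secondary parameters SAP 2.6 adds: "For the remaining parameters of efficacy, safety and tolerability, data replenishment is not provided".

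Criterion 2 exclusions are compared between arms only inside a safety drop-out rate that also contains criteria 3, 6 and 7.

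**The concern.** A tablet count measures rescue need only if a patient with more need records more tablets. Here the link breaks for the patients who do worst. One whose pain defeats paracetamol moves to an NSAID and stops adding paracetamol tablets. One who needs rescue most days is excluded and stops adding any. A low count can therefore mean little pain or failed paracetamol.

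The plan has no adjustment for time on study, no combined rescue measure, and no statement of whether a count cut short stands as the Week 25 value. At stake is the goal 2 conclusion: a true reduction in rescue need could be missed or appear reversed, or a paracetamol-sparing effect could be reported for a device whose patients more often failed paracetamol.

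**Working it through.** The plan gives no figure for rescue use; its only calculation is the primary-endpoint sample size. From the documents come 72 patients per arm, 24 weeks from day 1 to Week 25, and two-sided 5% tests. Every rescue, step-up and exit rate below is an assumption.

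**1. Single patients** (4 tablets per rescue day)

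| Patient | Rescue days/week | Paracetamol tablets at Week 25 | Rescue days per week observed |
|---|---|---|---|
| Stays on paracetamol | 2 | 2 × 4 × 24 = 192 | 2 |
| Moves to NSAID after week 5 | 2.5 | 2.5 × 4 × 5 = 50 | 2.5 |
| Excluded after week 2 | 4 | 4 × 4 × 2 = 32 | 4 |

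The count ranks the three in the reverse order of need.

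**2. Arm means, step-up only.** If a proportion p switches for good at week 5 on average, each switcher loses 24 − 5 = 19 weeks. Expected tablets = 4 × days per week × (24 − 19p).

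*Device better* (2.0 v 2.5 days a week, a true −20%), device p = 10%: device mean = 8 × (24 − 1.9) = 176.8.

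| Placebo p | Placebo mean | Device v placebo |
|---|---|---|
| 10% | 10 × 22.1 = 221 | −20% |
| 20% | 10 × 20.2 = 202 | −12% |
| 30% | 10 × 18.3 = 183 | −3% |
| 40% | 10 × 16.4 = 164 | +8% |

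The sign reverses when 10(24 − 19p) < 176.8, that is p > 0.333. It is 0.298 if all switch at week 2 and 0.380 if at week 8.

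*Equal need* (2.5 days in both arms), placebo p = 10%: device p = 20% gives 202/221, 9% lower on device; device p = 30% gives 183/221, 17% lower. Nothing differs but the step-up rate.

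**3. Test results for the same setting.** Simulated with gamma-distributed patient rates (shape 2, capped at 7 days), switch at weeks 2–8 and an unadjusted t-test. With the device better, power at placebo step-up 10/20/30/40% is 38/14/3/0.5%, and significance in the wrong direction occurs in 0/0.2/1.5/9% of runs. With equal need, the count falsely favours the device in 10% of runs at 20% v 10% step-up and about 30% at 30% v 10%, against a nominal 2.5%.

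**4. Criterion 2 applied week by week.** A second model uses 3 tablets per rescue day, need-driven step-up, counts kept at exit, and 1000 runs.

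| Scenario | Stepped up, device/placebo | Count without stopping | Count observed | Significant for device / placebo |
|---|---|---|---|---|
| Device better, same step-up hazard | 48/56% | 65 v 89 | 40 v 46 | 24% / 0.2% |
| Device better, placebo steps up more | 24/71% | 65 v 89 | 50 v 37 | 0% / 72% |
| Device worse, device steps up more | 71/24% | 89 v 66 | 37 v 50 | 75% / 0% |
| Equal need, device steps up more | 67/27% | 77 v 77 | 35 v 56 | 98% / 0% |
| Equal need, extra device exits 1% a week | 24/27% | 77 v 77 | 50 v 56 | 14% / 0.1% |

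In the first row the uninterrupted count would have had 77% power. Treating leavers as missing brings the last row back to 2.8% but leaves the fourth at 97%. A rule for leavers alone does not remove the step-up bias.

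**5. By visit.** With 10% v 20% step-up and switch weeks spread over 2–8, the true −20% becomes −19% at Week 6 (39.3/48.3), −15% at Week 13 (90.4/106.0) and −12% at Week 25 (176.8/202.0).

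**6. Alternative measure.** Days with any rescue drug per week observed kept 42–47% power in the device-benefit scenarios run, with no wrong-direction significance, against 2–37% for the count. Its two-sided error at equal need was about 5%.

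**The case against.** **Much is already visible.** The NSAID count and a drop-out rate containing criterion 2 are tested beside the paracetamol count. This stands in part: a careful reader would see NSAID use by arm. But no rule says the results must be read together, and criterion 2 is hidden in a pooled rate.

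**NSAID dose is a covariate.** SAP 2.3 lists total NSAID dose as a covariate in the sample size assumptions. SAP 2.1.2 does not carry it into the analysis model, and adjusting for a quantity that treatment itself may change would not be a clean cure.

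**Stopping need not be permanent, and leavers may simply be missing.** The ban is on combination; a patient may return to paracetamol. The simulations assume a lasting switch and so lean towards larger effects. Missing is also the more natural reading of SAP 2.6. Both points reduce the size without removing the mechanism.

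**A fuller plan may exist.** SAP 2.1 calls itself brief and refers to one. A rule may be there.

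Two stronger readings are tempting. First, a reader might infer that the counts always understate a device benefit, so that the harm is chiefly lost power. That presumes that the device works and that placebo patients step up or leave more. The rules apply equally to both arms, and nothing in the documents fixes which arm does so. Second, a reader might tie the size to the plan's ceiling, "Drop-outs during the study will not exceed 10" percent. Excluding only patients whose long-run average is 4 or more days (means 1.8 v 2.25 days a week) gives 6.4% v 13.0%, which looks like a match. Applying criterion 2 week by week to the same model gives about 28% v 39%, so that calibration fails.

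**Conclusion.** The concern holds as a bias of unknown size and unfixed direction. The mechanism follows from the protocol's rescue and exclusion rules, and nothing in the SAP provided offsets it. Its size depends on rescue, step-up and exit rates that the documents do not give, so the figures above show what is possible, not what to expect. With similar step-up in both arms and few exclusions, the distortion is small. With clearly unequal step-up, it can reverse a true benefit or create a false one. A larger sample would not cure this.

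Week 25 is most exposed and Week 6 least. The severity is minor: goal 2 is affected; the primary analysis and sample size are not. Confidence is medium, because the fuller plan and the diary layout are not among the documents.

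**What to change.** Leave the rescue and exclusion rules as they are. In SAP 2.1.3:

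1. Make the goal 2 measure the number of days with any rescue drug (paracetamol or a permitted NSAID) per week observed, from day 1 to each visit or early exit, compared with the planned model. Patients who leave early contribute their observed rate.
2. Report beside it, as supportive and by the planned chi-square test, the proportion with any NSAID use or criterion 2 exclusion. Show criterion 2 separately from criteria 3, 6 and 7. This proportion is a poor main measure: its power is 39% at 10% v 20% step-up with 72 per arm, but only 8–22% when step-up is equal, and it ignores paracetamol use short of criterion 2.
3. Keep both tablet counts as supportive. State that a lower paracetamol count is not read as less rescue need unless NSAID use and criterion 2 exclusions agree.

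The cost is one or two extra secondary analyses, a few sentences, and a check that the diary records days of intake. Applying criterion 2 already requires days-per-week information. If the diary does not give it, use the supportive proportion together with tablets per week observed.

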- Change of stiffness (WOMAC-B) and functionality (WOMAC-C) subscale scores on Visit 3 (Week 6), Visit 4 (Week 13) and Visit 5 (Week 25) in comparison with baseline on Visit 1 (Week 1);
- Patient's assessment of the treatment efficacy, value OEP (per scale from 1 evident aggravation to 6 significant improvement) on Visits 5, 6 and 7 (values OEP-w₆, OEP-w₁₃, OEP-w₂₅);
- Investigator's assessment of the treatment efficacy, value OEI
 (per scale from 1 evident aggravation to 6 significant
 improvement) on Visits 3, 4 and 5 (values OEI-w₆, OEI-w₁₃, OEI-w₂₅);
- Assessment of the total number of paracetamol tablets taken (one tablet = 500 mg) beginning from day 1, on Visits 3, 4 and 5 (values PARACETAMOL-w₆, PARACETAMOL-w₁₃ and PARACETAMOL-w₂₅, correspondingly);

- Assessment of the total number of NSAID tablets taken starting from day1, on Visits 3, 5 and 5 (values NSAID-w₆, NSAID-w₁₃, NSAID-w₂₅ correspondingly);
- Patient exclusion rates due to safety (subject exclusion criteria 2, 3, 6, 7);
- Patient exclusion rates due to poor patient's treatment compliance (criteria 4 and 5).

Safety assessment parameters:

- Frequency of AE and/or SAE reporting in treatment groups;
- Global study physician and patient assessment of the therapy intolerability;
- Vital signs (HR, BP, body temperature, RR);
- Laboratory test results.

AE description will be presented per the following scheme:

- AE description;
- Severity of manifestation;
- Duration:
- Relationship with the study product;
- Outcome.

AE will be encoded in accordance with the Medical Dictionary for Regulatory Activities MedDRA.

Inclusion criteria

- 1) Men and women above 50 years;
- 2) Verified knee osteoarthritis in accordance with the ACR criteria (knee pain combined with one of the following signs: age above 50 years, knee crepitus or morning joint stiffness lasting for less than 30 minutes combined with radiologic signs of knee osteoarthritis);
- Kellgren Lawrence radiological grade II-III knee osteoarthritis with the predominant involvement of the medial tibiofemoral region of the knee joint;
- 4) Joint space width (JSW) of the target knee joint at least 2.5 mm.

Non-inclusion criteria

 History of any injury or surgical intervention on the target knee joint (except for diagnostic arthroscopy made more than 60 days before study entry);

- Severe degenerative changes in the target knee joint determined as the joint space narrowing less than 2 mm;

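### The secondary rate of drop-out 'due to safety' counts exclusions for analgesic need from knee osteoarthritis, so it mixes symptom control with harm

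*SAP*

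**What the plan says.** SAP 2.1.3 includes among the secondary efficacy parameters "Drop-out rate due to safety (exclusion criteria 2, 3, 6, 7"), and compares frequency indicators between groups by chi-square. The protocol synopsis has the same item among its secondary endpoints: "Patient exclusion rates due to safety (subject exclusion criteria 2, 3, 6, 7").

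The synopsis list of subject exclusion criteria gives the four components:

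- Criterion 2: "Need in paracetamol or NSAID intake due to knee osteoarthritis 4 days a week or more during 2 successive weeks".
- Criterion 3: "The investigator makes the decision that a patient should discontinue the study in the best interests of the patient".
- Criterion 6: "Individual intolerability or contraindications to the study MD, placebo or paracetamol".
- Criterion 7: an AE or SAE whose work-up or treatment significantly affects the study procedures.

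Two other places place analgesic need outside safety. The study goals list "Assessment of the need in paracetamol and NSAID (in case of ineffective therapy with paracetamol) intake to relieve the knee pain" as a goal of its own, with safety as a different goal. SAP 2.1.3 has, as a further secondary efficacy parameter, "Assessment as per patient diary of the total number of paracetamol tablets taken", and a matching count for NSAIDs.

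The supplied text plans no breakdown of exclusions by criterion. SAP 2.1 describes itself as brief and leaves the full analysis to a later document.

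**The concern.** A rate labelled 'due to safety' will be read as withdrawal because of harm. Criterion 2 is a threshold on symptomatic treatment for the disease under study, so it responds to efficacy. The components can move in opposite directions. A device that relieves pain would leave more criterion 2 exclusions on placebo, while intolerance and injection-related events would add exclusions on the device.

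Two misreadings follow. Equal pooled rates could be taken as equal withdrawal for safety when they are not equal. A lower pooled rate on the device could be reported as a safety advantage when it is a symptom effect.

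**Working it through.** **Step 1: match the criteria to the label.**

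| Criterion | What it captures | Harm only? |
|---|---|---|
| 2 | Analgesic need from knee osteoarthritis | No, mainly symptom control |
| 3 | Investigator's decision | No, could be harm or lack of effect |
| 6 | Intolerance or contraindication to device, placebo or paracetamol | Mixed, since it includes paracetamol |
| 7 | AE/SAE | Yes |

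Both documents use the same four numbers, so this is the operative definition and not a slip in one list. Criterion 2 is not purely lack of effect either. The protocol's text on unscheduled visits gives as reasons "aggravation of the studied medical condition, AE or intolerability of the study MD or placebo therapy", so a flare after an injection could lead to it. Removing criterion 2 alone would therefore not leave a pure harm rate.

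**Step 2: inputs for an illustration.** There are 72 randomised per arm (SAP 2.3). The drop-out allowance is 10%, that is 0.10 × 144 = 14.4 patients. The plan states no expected rate for any criterion, so there is no figure of its own to reproduce. All counts below are assumptions, with one criterion per patient.

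**Step 3: formula.** With a and b exclusions in arms of 72 and m = a + b, the Pearson chi-square without continuity correction is 144(a − b)² / [m(144 − m)]. For 6 v 1 it is 144 × 25 / (7 × 137) = 3600 / 959 = 3.754, p = 0.053. Intervals for the difference are Newcombe 95%.

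**Step 4: results (device v placebo).**

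| Scenario | Criteria 3/6/7 | Criterion 2 | Pooled rate |
|---|---|---|---|
| Cancelled, high end | 6 v 1: +6.9 points (-0.6 to 15.7), p = 0.053, Fisher 0.116 | 1 v 6 | 7 v 7: 0.0 (-10.3 to 10.3), p = 1.0 |
| Cancelled, fewer events | 4 v 1: +4.2 (-2.8 to 12.1), p = 0.172, Fisher 0.366 | 1 v 4 | 5 v 5: 0.0 (-9.2 to 9.2), p = 1.0 |
| No offset | 4 v 1: +4.2 | 2 v 2 | 6 v 3: +4.2, p = 0.302, Fisher 0.494 |
| Created | 2 v 2: 0.0 | 1 v 5 | 3 v 7 (4.2% v 9.7%): -5.6, p = 0.19, Fisher 0.33 |

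The high-end case uses 14 exclusions, nearly all of the 14.4 allowed. The fewer-events case uses 10.

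**Step 5: power.** By binomial enumeration with chi-square at 0.05, a comparison of criteria 3/6/7 alone has power 15% at 5% v 2% and 55% at 10% v 2%. Separating the criteria would not give a powerful safety test. What pooling loses is mainly the meaning of the rate.

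**The case against.** The strongest reply is that harm is assessed elsewhere. The protocol's separate list of safety assessment parameters does not contain this rate, and SAP 2.1.4 compares AE, SAE, laboratory, vital-sign and tolerability frequencies by arm. A criterion 7 exclusion is by definition an AE or SAE and would appear there. This stands and limits the consequence. It does not make the rate interpretable: SAP 2.1.4 lists no withdrawals by reason, and a criterion 3 exclusion need not be an AE.

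The grouping may also be deliberate. The telephone contacts put any AE and sustained analgesic need in one trigger for an extra visit, which suggests patient protection. That may explain the label, but the plan's own goals and efficacy parameters still classify analgesic need differently.

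A breakdown may exist in text that was not supplied, since SAP 2.1 defers the full analysis. The pooling is certain and the absence of a breakdown is not. A table by criterion would remove most of the practical harm, but the label would still be wrong.

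Finally, every count is assumed, the two cancelling cases were chosen to cancel exactly, and even the 6 v 1 contrast is not significant. This is fair. The counts show what the rate can do, not what it will do. The high-end case also leaves almost no room within the 10% for any other reason for drop-out.

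**Conclusion.** The point holds. By the documents' own classification, one tested secondary rate labelled as safety contains a symptom-control component, and two of its other components are also not specific to harm. Under assumed counts within the 10% drop-out allowance, pooling can reduce a difference of 4.2 to 6.9 points in criteria 3/6/7 to zero, or produce an apparent advantage of 5.6 points for the device when those criteria are equal. How far this happens depends on whether criterion 2 exclusions lean towards placebo, which the documents do not allow one to predict. The primary analysis and the sample size are not affected. The change should be made, because it is cheap and the rate cannot be read as labelled.

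**What to change.** In both endpoint lists (protocol synopsis, secondary endpoints; SAP 2.1.3):

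1. Take criterion 2 out of the 'due to safety' rate.
2. Report it as its own rate under a neutral label, such as 'exclusion for analgesic need due to knee osteoarthritis', with the same chi-square comparison.
3. Add one descriptive table of exclusions by individual criterion and arm, so that criteria 3 and 6 can be read separately. If such a table is already planned elsewhere, refer to it here.

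The exclusion rule is unchanged; only the reporting changes. As a separate matter, the telephone-contact text puts the analgesic threshold at more than 4 days a week, while criterion 2 includes 4 days. These passages must be reconciled, and the mismatch affects the existing pooled rate just as much.

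The cost is wording in two lists and one table. The downside is one more comparison with few events, so both rates should be read mainly as estimates with confidence intervals. SAP 3.2 says only that the eCRF holds data on completion of participation, so confirm that it records which exclusion criterion applied. The present rate already needs that information.
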